#### Pharmacodynamic assessments:

Pharmacodynamic assessments will be performed at specified time points per the Schedule of Assessments and will include fasting (at least 8 hours) LDL-C, total cholesterol, non-HDL-C, HDL-C, VLDL-C, triglycerides, retinol, retinol binding protein, cytokines, cytokeratin-18, blood exosomal HSD17β13 and PNPLA3 mRNA (if feasible), liver biopsy tissue PNPLA3 mRNA, liver biopsy tissue PNPLA3 and HSD17β13 protein levels (if feasible), hemoglobin A1C, serum glucose, PRO-C3, ELF, MRI-PDFF and Fibroscan. All serum tests will be completed after an 8-hour fast unless as otherwise specified. Results, percent change, and duration of response (when applicable) from baseline to 4 weeks (or longer as necessary) will be analyzed and summarized by dose cohort and treatment group. For lipid related and serum pharmacodynamic assessments, baseline is defined as the pre-dose value obtained nearest to the first dose.

#### Immunogenicity:

Samples will be collected for anti-drug antibody testing for cohorts (NASH patients only) at pre-dose, day 57, and EOS, or at Early Termination as per Schedule of Assessments.

#### Pharmacokinetics & Urine/Plasma Drug Metabolites:

Blood and urine samples will be collected for pharmacokinetic and drug metabolite analysis per the Schedule of Assessments.

Arrowhead Pharmaceuticals, Inc. Protocol No.: AROHSD1001

Table 1 Schedule of Assessments for Cohorts 1-4 Single Dose: NHV

A	Screening						Day 1					24 hr								End of	
Assessment	(Day -45	Pre-	0	15	30		Day 1					post-			Day	Day	Day	Day	Day	Study (or Early Term)	90 days
	Day -1)	dose	min	min		1 hr	2 hr	4 hr	8 hr	12 hr	18 hr		48 hr	Day 8		29			85, 99		after EOS
Visit Window		-2hrs	±2 n	ninutes	s PK c	nly, ±	10 mi	nutes	other j	proced	dures	±1	hr	±2d	±7d						
Informed Consent	X																				
Eligibility Criteria	X																				
Demographics/Medical Hx	X																				
Physical Exam (See Section 10.3.2)	X	X										as needed		as needed	as needed	as needed	as needed	as needed	as needed	X	
BMI	X	X																		X	
Concomitant Meds/Therapies	X	X										X	X	X	X	X	X	X	X	X	
Electrocardiogram (See Section 10.3.3)	X	X				X	X					X	X			X				X	
Urine Pregnancy Test (WOCP) confirmed negative pre-dose	X	X																		X	
FSH (post-menopause)	X																				
Urine Drug Screen	X																				
Vitals (BP, temp, HR, RR, O 2 )	X	X			X	X	X	X	X			X	X	X	X	X	X	X	X	X	
HIV, Hep B, C	X																				
Labs (heme, coag, lipase, chem, lipids)	X	X										X	X	X	X	X	X	X	X	X	
Hemoglobin A1c	X	X																		X	
Blood PK including met ID		X		X	X	X	X	X	X	X	X	X	X	X	X	X					
Urine PK including met ID		spot		Day 1	0-4 h	r, 4-12	hr, 1	2-24 l	r urin	e colle	ections	S	spot	spot	spot	spot					
Urinalysis	X	X										X	X	X	X	X	X	X	X	X	
Administration of ARO-HSD			X																		
Adverse Events Collection	Х –																			X	
Pregnancy phone call																					X

Page 9 of 59

Table 2 Schedule of Assessments for Cohorts 1b, 3b, 4b: Subjects with suspected NASH (biopsies on screen and day 71)

Confidential

Assessment	Screening			Da	y 1		24 hr						End of Study (or	
Assessment	(Day -60	Pre- dose	0 min	30 min	1 hr	2 hr	post- dose	Day 15	Day 29	Day 57	Day 71	Day 85	Early Term) Day 113	90 days after EOS
Visit Window	Day -1)	-2hrs	±2m	nin (PK o	nly), ±10	)min	±1hr	±2d	±2d	±2d	±5d	±2d	±5d	±7d
Informed Consent	X													
Eligibility Criteria	X													
Demographics/Medical Hx	X													
Physical Exam (See Section 10.3.2)	X	X					as needed	as needed	as needed	as needed	as needed	as needed	X	
BMI (Height and Body Weight)	X	$X^1$							$\mathbf{X}^{1}$		$X^1$		$X^1$	
Concomitant Meds/Therapies	X	X					X	X	X	X	X	X	X	
Electrocardiogram (See Section 10.3.3)	X	X			X	X	X		$(0, 1, 2hr)^2$				X	
Urine Pregnancy Test (WOCP) confirmed negative pre-dose/pre-bx	X	X							pre-dose		pre-bx		X	
FSH (post-menopause)	X													
Urine Drug Screen	X													
Vitals (BP, temp, HR, RR, O 2 )	X	X		X	X	X	X	X	X	X	X	X	X	
HIV, Hep B, C	X													
Labs (heme, coag, chem, lipase, lipids)	X	X					X	X	X	X	X	X	X	
Retinol, RBP, blood for exosomes, cytokine panel		X						X	X	X	X	X	X	
Hemoglobin A1c	X	X											X	
Pro-C3, ELF, Cytokeratin-18		X											X	
Blood PK		X		X	X	X	X	X	pre-dose					
Genotyping (HSD17β13, PNPLA3)	X													
Urinalysis	X	X					X	X	X	X	X	X	X	
Liver Biopsy, FibroScan, MRI-PDFF	X 										X			
Administration of ARO-HSD			X						X					

<sup>1 Body weight only  10-minute window allowed

<sup>3 Liver biopsy can be done at D1, as long it is completed prior to any D1 procedures Version 7.0, 12 March 2021

Arrowhead Pharmaceuticals, Inc. Protocol No.: AROHSD1001

Confidential

Page 11 of 59

Anti-Drug Antibodies		X				X		X	
Adverse Events Collection	х –							X	
Pregnancy phone call									X

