#### **Cohort Summary**

Cohort	Population	Blinding	# Subjects	Dosing Schedule
1	NHVs	Double blind	8 (4 active:	25 mg Day 1 only
			4 placebo)	
1b	Patients with suspected NASH	Open Label	up to 6	25 mg Days 1, 29
	(biopsies on screen and day 71)		(all active)	
2	NHVs	Double blind	8 (4 active:	50 mg Day 1 only
			4 placebo)	
3	NHVs	Double blind	8 (4 active:	≤ 100 mg Day 1 only
			4 placebo)	
4	NHVs	Double blind	8 (4 active:	$\leq$ 200 mg Day 1 only
			4 placebo)	
3b	Patients with suspected NASH	Open Label	up to 6	≤100 mg Days 1, 29
	(biopsies on screen and day 71)		(all active)	
4b	Patients with suspected NASH	Open Label	up to 6	≤200 mg Days 1, 29
	(biopsies on screen and day 71)		(all active)	

Approximately 50 subjects may be enrolled in the study (not including replacements or optional expansion cohort).

**Number of Doses per Treatment:** Single dose (Cohorts 1, 2, 3, 4) or two doses (Cohorts 1b, 3b and 4b) dosed 28 days apart

**Study Duration:** For subjects in Cohorts 1 through 4, the duration of the study clinic visits is approximately 158 days from screening to the End-of-Study visit. For subjects in Cohorts 1b, 3b and 4b, the duration of the study clinic visits is approximately up to 173 days from screening to the End-of-Study visit. Additionally, all subjects will have a 90-day post-end of study visit follow-up phone call assessing compliance with contraception.

**Study Confinement:** For all NHV cohorts (1-4), clinical facility confinement will be approximately 3 days for dose administration (Day -1 through 24-hour assessments) with discharge on Day 2. Subjects will return to the clinical facility for outpatient visits per the Schedule of Assessments. Patients in Cohorts 1b, 3b and 4b will be at the facility for approximately 4 hours (2 hours before dosing and 2 hours after dosing) on dosing days.

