#### 10.5 Study Treatment Administration

Appropriately trained employees of the clinical site will administer the study treatment. Each dose will be administered as a single subcutaneous injection. The date, time and location of administration will be recorded in the source notes and witnessed by a second person from the clinical facility. The site of injection will be marked and mapped for later observation. The preferred site of injection is the abdomen. Optional additional sites are the upper arms and thighs.

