# 11.5.2 AEs at the Injection Site and Local Injection Site Reactions (LISRs)

AEs at the injection site will be graded as either Mild, Moderate or Severe. A local injection site reaction is defined as an adverse reaction (usually immunologic) developing at the site of injection and lasting at least 48 hours. For the data reporting and analysis purposes, the definition of LISR based on duration of at least 48 hours and based on the specified MedDRA preferred times is provided in Appendix 16.2. Photographs of local reactions around injection site should be obtained at the time of reporting and at the approximate time of resolution.

- Mild: Tenderness with or without associated symptoms (e.g., warmth, erythema, itching), mild pain or mild edema
- Moderate: Pain with associated phlebitis or lipodystrophy
- Severe: Tissue ulceration or necrosis with associated severe tissue damage or if operative intervention is indicated

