# 16.2 Local Injection Site Reactions (LISRs)

The following MedDRA Preferred Terms determined by the Sponsor's pharmacovigilance personnel represent the local injection site reaction:

Injection site discomfort	Injection site abscess
Injection site discoloration	Injection site abscess sterile

Injection site erythema	Injection site atrophy
Injection site irritation	Injection site calcification
Injection site inflammation	Injection site cellulitis
Injection site induration	Injection site dermatitis
Injection site pain	Injection site erosion
Injection site oedema	Injection site fibrosis
Injection site pruritus	Injection site indentation
Injection site rash	Injection site necrosis
Injection site urticaria	Injection site nodule
Injection site reaction	Injection site ulcer
Injection site swelling	

LISRs will only include events that start on the day of injection and persist for at least 48 hours post injection (i.e., event onset date on the day of injection and resolution date not on the day of injection or the day after the injection) will be included. Events with onset date on the day of injection and missing resolution date will also be included in the summary.

The following calculation will be utilized to determine the percentage of injections leading to local injection site reactions:

 $(A/B)^*$ , where A = number of injections with a local injection site reactions, and B = total number of injections.

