5. DEFINITIONS

Day 1:

For each subject, Day 1 is defined as the first day that protocol-specified study treatment is administered to the subject.

End of Study (EOS) Date:

For each subject, the EOS date is the study completion/early termination date recorded on the eCRF.

Study Day:

For each subject, and for a given date of interest, study day is defined as the number of days relative to Day 1:

- After first dose date: study day = date of interest – Day 1 date + 1
- Prior to first dose date: study day = date of interest – Day 1 date, so that the day prior to Day 1 is Day -1

Study End Date:

The study end date is when the last subject finishes the EOS visit.

Baseline Values:

For all variables, baseline is defined as the last non-missing value obtained prior to the first dose administration on Day 1.

For ECG, if a triplicate is taken prior to the first dose administered on Day 1, baseline is defined as the mean over the set of triplicate assessments.

Analysis Day:

Selected endpoints will be summarized based on Analysis Day defined using Study Day as below.

Scheduled Visit/ Analysis Day	Day 8	Day 15	Day 29	Day 43	Day 57	Day 71	Day 85	Day 99	Day 113
Study Day Window Cohort 1-4	[6,10]	[13,17]	[27,31]	[41, 45]	[55,59]	[69,73]	[83,87]	[97,101]	[111,115]
Study Day Window Cohort 1b,3b,4b	NA	[13,17]	[27,31]	NA	[55,59]	[66,76]	[83,87]	NA	[108,118]

If there is more than one record in a study day window, the analytical record for that specific analysis day will be defined as the record closest to the scheduled visit day. If two records are equidistant from the scheduled visit day, then the earlier record will be chosen. If there are multiple records on the same day, the last record will be used.

Duration of study:

EOS date – Day 1 date + 1

Treatment-Emergent Adverse Event (TEAE):

TEAEs are defined as adverse events occurring on or after the first dose of study treatment through EOS or pre-treatment existing conditions that worsen after the investigational product administration.

Treatment-emergent SAEs (TESAEs):

TESAEs are defined as serious adverse events occurring on or after the first dose of study treatment through EOS or pre-treatment existing conditions that worsen after the investigational product administration.

TEAE at Injection Site:

TEAE occur at the injection site. MedDRA Preferred Terms which are included in LISR are listed in Protocol Section 16.2.

TEAE Related to Local Injection Site Reaction (LISR):

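### After the second dose (Day 29) the patient cohorts have no scheduled contact until Day 57, so adverse events first noticed after discharge depend on spontaneous report or about four weeks' recall

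*Protocol*

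**What the plan says.** The patient visits are in Protocol Table 2, "Table 2 Schedule of Assessments for Cohorts 1b, 3b, 4b: Subjects with suspected NASH (biopsies on screen and day 71"). After Day 1 its columns are 24 h post-dose, Day 15, Day 29, Day 57, Day 71, Day 85 and Day 113. Doses are given on Days 1 and 29, and the 24 h column belongs to Day 1 only. On Day 29 the only timed post-dose items are ECGs, the last at 2 h. PK is pre-dose only. Patients "will be at the facility for approximately 4 hours (2 hours before dosing and 2 hours after dosing) on dosing days" (Synopsis, Study Confinement). In SAP 5, the row "Study Day Window Cohort 1b,3b,4b" marks Day 43 as not applicable. The only scheduled telephone call comes 90 days after end of study and concerns contraception.

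Healthy volunteers follow "Table 1 Schedule of Assessments for Cohorts 1-4 Single Dose: NHV", which has 24 h, 48 h and Day 8 visits after their single dose.

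Adverse events are collected from consent to end of study and are evaluated at each visit (Protocol 11.3). The investigator is on call throughout (10.1) and must actively follow an event once it is known (11.6).

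For injection sites, Protocol 10.5 says: "The site of injection will be marked and mapped for later observation". Protocol 11.5.2 adds: "Photographs of local reactions around injection site should be obtained at the time of reporting and at the approximate time of resolution". The local injection site reaction (LISR) rule in Protocol 16.2 is: "LISRs will only include events that start on the day of injection and persist for at least 48 hours post injection". It continues: "Events with onset date on the day of injection and missing resolution date will also be included in the summary". SAP 5 words the onset differently and places it on the day after injection.

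**The concern.** The primary endpoint is treatment-related adverse events, and in patients it is framed around multiple doses (Protocol 6.1). Cohorts 1b, 3b and 4b are the only repeat exposure in this first-in-human study. The weeks just after re-exposure nevertheless have the thinnest scheduled follow-up of any post-dose period. Continuous collection on paper does not supply an occasion to ask, because events are elicited and assessed at visits.

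Transient symptoms and injection-site reactions are the events most easily lost. Protocol 5.7 names injection-site reactions as a known risk of this drug type and promises photographs to track them. A reaction that starts after the patient goes home from dose 2, and is not phoned in, would be asked about on Day 57 at the earliest. It may then be forgotten, or recalled without a reliable stop date. Under Protocol 16.2 a missing stop date makes a reaction with injection-day onset count as an LISR, so error in the LISR table can run either way.

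**Working it through.** **Check that Table 2 is read correctly.** The plan gives about 173 days from screening to end of study for patients: 60 + 113 = 173. For volunteers it gives about 158: 45 + 113 = 158. Both reproduce.

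**Length of the gap** (Day 29 and Day 57, each ±2 days; SAP 5 windows 27 to 31 and 55 to 59):
- nominal: 57 − 29 = 28 days
- shortest: 55 − 31 = 24 days
- longest: 59 − 27 = 32 days

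**Scheduled contacts in the 28 days after a dose** (Tables 1 and 2, read with the SAP 5 windows):

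| Group and dose | Contacts | Number |
|---|---|---|
| Volunteers, single dose | 24 h, 48 h, Days 8, 15, 29 | 5 |
| Patients, dose 1 | 24 h, Days 15, 29 | 3 |
| Patients, dose 2 | Day 57 | 1 |

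**Doses affected.** 3 cohorts × 6 = 18 second doses, which is 18 of 36 planned patient injections. With two extra patients in each of 1b and 3b: 18 + 4 = 22 of 44.

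**The 48 h point.** After dose 1, patients are seen at 24 h and then on Day 15, so no contact falls near 48 h there either. This weakness is common to both doses. What is particular to dose 2 is the absence of a next-day contact and of a contact at about two weeks.

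**When a call can settle the LISR rule.**
- Protocol 16.2: onset on the injection day and lasting at least 48 h. Its date form requires resolution later than the day after injection. The latest injection-day onset is under 24 h after dosing, so even 48 h counted from onset is complete before 24 + 48 = 72 h.
- SAP 5: onset on the day after injection, lasting at least 48 h. That day ends less than 48 h after dosing, so the required persistence can run to just under 48 + 48 = 96 h. For example, with a 09:00 dose and onset at 20:00 the next day (35 h), the 48 h are complete at 35 + 48 = 83 h.

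A call at 48 to 72 h therefore does not cover the SAP wording. A call at 96 h covers both.

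**Effect of the calls on the gap.** With dose 2 on Day 29, calls on Days 33 and 43 split the 28 days into 4, 10 and 14. The longest unobserved stretch halves to 14 days.

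**Scale of one patient.** 1/6 = 16.7 points, or 1/8 = 12.5 points in a cohort of eight. These figures show only how coarse the cohort percentages are. The documents give no event rates, so the number of events missed cannot be calculated.

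**The case against.** The strongest reply is that this is a legitimate design choice. The second dose repeats a level that the same patient has already received and that volunteers received first. The volunteers' dense early visits also serve PK and metabolite sampling. Collection is continuous, the investigator is on call, and serious or persistent events would probably surface. A reaction visible in the 2 h stay must be followed to resolution under Protocol 11.6. All of this stands, and it narrows the concern to events first noticed after discharge and not reported spontaneously.

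Three stronger readings are tempting and are not supported.

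- A reader might infer that events after dose 2 are not collected or not analysed. They are: SAP 5 counts events from first dose to end of study as treatment-emergent, and SAP 9.6.1 tabulates them. They are simply not shown by dose.
- A reader might infer that a misclassified LISR distorts the primary endpoint. It does not. A reported reaction judged related counts as a related event whatever its duration, and only the LISR results change.
- A reader might take 16.7 or 12.5 points as the size of the bias. They are 1/n and measure nothing about this gap.

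The reply also notes that all patient cohorts now share one schedule, and that Cohort 1b (25 mg) enrolls after 3b and 4b. Calls added late would mainly give the lowest dose closer ascertainment. That is correct, and it must be disclosed.

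**Conclusion.** The concern holds in a limited form. Table 2 and the SAP windows agree that no contact is scheduled from about 2 h after the Day 29 dose until Day 57: 28 days, range 24 to 32, for up to 18 patients (22 with extras). Ascertainment of events first noticed after that discharge rests on spontaneous report or on about four weeks' recall. The lack of a contact near 48 h applies to both doses and bears on LISR classification alone.

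The conclusion assumes that no diary or call is prescribed in a manual outside these documents; none appears in the protocol or SAP. Confidence is high for the schedule itself. The size of any under-count is unknown. The documents do not support a claim that multiple-dose safety cannot be assessed. The point is worth acting on where patients remain, at the level of something to consider or, at most, a mild recommendation.

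**What to change.** 1. For patients not yet past Day 57, add to Table 2 a telephone adverse-event and injection-site query about 4 days (96 h) after the Day 29 dose and another near Day 43. Record onset and stop dates.
2. For patients who have not yet had dose 1, add the same 4-day call after Day 1, so that the two doses are followed alike around the LISR decision point.
3. Change the LISR onset in SAP 5 to the day of injection, as in Protocol 16.2, before any LISR is tabulated.
4. If every patient is already past Day 57, state the gap as a limitation beside the patient adverse-event tables.

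Cost: two or three short calls per remaining patient, plus the amendment to Table 2. If only Cohort 1b remains, that is 2 × 6 = 12 to 2 × 8 = 16 calls where dose 1 has already been given, or 3 × 6 = 18 to 3 × 8 = 24 where it has not. The main downside is closer ascertainment in Cohort 1b than in 3b and 4b. Footnote this wherever adverse-event rates are compared across doses. The calls will not detect symptom-free laboratory changes, since no blood draw is scheduled between Days 29 and 57.

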## 5.7 Risk Assessment for Participants

- **Embryo-Fetal:** Limited GLP toxicology studies have been conducted. Accordingly, eligible participants enrolled in this study, both male and female (including partners), must agree to use two highly effective forms of contraception during the study and for 3 months post-dose, or agree to abstinence (acceptable only if this method is in alignment with the normal life style of the patient).
- **Hepatic:** ARO-HSD targets the liver. siRNA literature has described ALT changes associated with off-target effects of the siRNA seed region on microRNAs in the hepatocyte (Janas, et al. 2018). The siRNA sequence of the ARO-HSD sense and antisense molecules have been screened for potential mRNA and microRNA homology and sequences with homology were excluded from consideration. Thus, no such off-target effects are anticipated. However, to mitigate this risk, the proposed study protocol has built in stopping rules for ALT and AST elevation. Blood samples will be drawn frequently to evaluate liver injury and liver function. The Data Safety Committee (DSC) will review all available safety data including laboratory data prior to dose escalation. Additionally, the planned starting dose of 25 mg is approximately 1/252nd (assuming weight-based conversion and a 70kg subject) of the No-Observed-Adverse-Effect-Level (NOAEL) of 90 mg/kg based on the rat GLP study and 1/840th of the 300 mg/kg monkey NOAEL. The highest planned dose in this study of 200 mg is 1/31st of the 90 mg/kg rat NOAEL and 1/140th of the monkey NOAEL. There is a wide margin of safety between planned clinical doses and animal toxicology study NOAELs.
- Injection Site Reactions: Other subcutaneously administered modified siRNA drug candidates evaluated in clinical studies have been associated with mild to moderate injection site reactions (e.g. pain, erythema). This study includes a protocol for evaluation and grading of injection site reactions based on predefined criteria for mild, moderate and severe. Injection site reactions will be photographed for tracking resolution and/or progression. Additionally, steps will be taken to minimize injection site reactions such as rotating injection sites and allowing the ARO-HSD solution to come to room temperature prior to injecting.

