#### 7. STUDY PLAN

## 7.1 Study Design

Participants who have signed an EC/IRB approved informed consent form and have met all the protocol eligibility criteria during screening may be enrolled into the study in a double-blind or open label fashion depending on the cohort. Cohorts 1 through 4 will begin with administration

of ARO-HSD or PBO to two sentinel participants (one ARO-HSD, one PBO). Following the Day 3 evaluation in these participants, if there are no significant safety concerns, the remaining participants in the cohort will be treated at the discretion of the Principal Investigator (PI). Dosing of participants will be staggered by at least 30 minutes such that no two participants will be dosed simultaneously. Sentinel dosing is not required in patient cohorts.

Dose levels by cohort are outlined in Table 4 and Figure 1. Cohorts 1 through 4 will enroll sequentially with patient cohorts opening for enrollment in a step-wise manner. Screening for all Cohorts may begin once Cohort 1 has been opened for enrollment.

Clinical facility confinement will be approximately 3 days for first dose administration in NHV cohorts (Cohorts 1, 2, 3, and 4) with discharge on Day 2. Subjects will return to the clinical facility for outpatient visits per the Schedule of Assessments. Subjects in cohorts 1b, 3b and 4b will be at the facility for approximately 4 hours (2 hours before dosing and 2 hours after dosing) on dosing days.

**Table 4** Cohort Summary

		T	I	
Cohort	Population	Blinding	# Subjects	Dosing Schedule
1	NHVs	Double blind	8 (4 active:	25 mg Day 1 only
			4 placebo)	
1b	Patients with suspected NASH	Open Label	up to 6	25 mg Days 1, 29
	(biopsies on screen and day 71)		(all active)	
2	NHVs	Double blind	8 (4 active:	50 mg Day 1 only
			4 placebo)	
3	NHVs	Double blind	8 (4 active:	$\leq 100 \text{ mg Day 1 only}$
			4 placebo)	
4	NHVs	Double blind	8 (4 active:	$\leq$ 200 mg Day 1 only
			4 placebo)	
3b	Patients with suspected NASH	Open Label	up to 6	$\leq$ 100 mg Days 1, 29
	(biopsies on screen and day 71)		(all active)	
4b	Patients with suspected NASH	Open Label	up to 6	≤ 200 mg Days 1, 29
	(biopsies on screen and day 71)		(all active)	

[figure not shown]

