# **10.3.5 Clinical Laboratory Tests**

Blood and urine samples will be collected to perform clinical laboratory tests. Participants will be required to fast for the screening and other pharmacodynamic sample collections.

Central labs will be utilized. However, local labs may be utilized as necessary if needed by the investigator or for emergent situations.

Within the screen period, up to 60 days prior to the first dose of study medication, a blood and urine sample will be collected for the laboratory tests detailed below to establish baseline data and eligibility for enrolment. One repeat Screening lab draw is allowed per assessment to

establish eligibility. The results will be assessed by the PI, or medically qualified designee, before study enrollment. Any abnormality in laboratory values (that are confirmed on repeat) deemed clinically significant by the PI, or medically qualified designee (i.e., those that would jeopardize the safety of the participant or impact on the validity of the study results), will result in exclusion of that participant. Clinical laboratory tests will be performed on participants' blood and urine at specified time-points listed in the Schedule of Assessments.

- *Biochemistry*: Sodium, potassium, chloride, bicarbonate, glucose, urea, creatinine (including calculated creatinine clearance), creatine kinase, phosphate, total calcium, albumin, total protein, total bilirubin, lipase and amylase, conjugated bilirubin, alkaline phosphatase (ALP), alanine aminotransferase (ALT), and aspartate transaminase (AST), hemoglobin A1C
- *Hematology:* Hemoglobin, red blood cell count (RBC), hematocrit, mean cell volume (MCV), mean cell hemoglobin (MCH), mean cell hemoglobin concentration (MCHC), platelets, white cell count, neutrophils, lymphocytes, monocytes, eosinophils and basophils
- Coagulation: Partial thromboplastin time (PTT), Prothrombin time (PT) with INR
- *Urinalysis:* Leucocytes, nitrites, urobilinogen, protein, pH, blood, specific gravity, ketone, bilirubin and glucose
- *Urine drug screen:* urine will be analyzed for benzodiazepines, amphetamines, methamphetamines, methadone, phencyclidine, barbiturates, opiates, cocaine, ecstasy and cannabinoids
- *Microscopic urinalysis will be performed if indicated:* white blood cells, red blood cells, epithelial cells, bacteria

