# 15. INFORMATION DISCLOSURE AND INVENTIONS

# 15.1 Ownership

# 15.2 Confidentiality

#### 15.3 **Publication**

# 16. APPENDICES

# 16.1 Study Modification Guidelines For Subjects And Patients With Baseline Pre-Dose Evidence Of Liver Disease

Treatment-Emergent ALT	Treatment-Emergent Total Bilirubin (TBL)	Liver Symptoms	Action
Normal baseline with treatment emergent (TE) increase to ALT > 5x ULN  Elevated baseline with TE increase to: ALT > 3x baseline or > 300 U/L (whichever occurs first)	Normal	None	Repeat ALT, AST, ALP, TBL, in 2–3 days Follow-up for symptoms.
Normal baseline with TE increase to ALT > 8x ULN  Elevated baseline with TE increase to: ALT > 5x baseline or > 500 U/L (whichever occurs first)	Normal	None	Interrupt study drug. Initiate close observation and workup for competing etiologies. (see below)  Study drug can be restarted only if an alternative etiology is identified and liver enzymes return to baseline.
Normal baseline with TE increase to ALT > 3x ULN  Elevated baseline with TE increase to ALT > 2x baseline or > 200 U/L (whichever occurs first)	TBL > 2x ULN	None	Interrupt study drug. Initiate close observation and workup for competing etiologies.  Study drug can be restarted only if an alternative etiology is identified and liver enzymes return to baseline.

Normal baseline with	Normal or elevated	Symptoms of	Interrupt study drug.
TE increase to ALT		clinical	Initiate close observation
> 3x ULN		hepatitis -	and workup for
		severe fatigue,	competing etiologies.
Elevated baseline with		nausea,	
TE increase to ALT >		vomiting,	Study drug should not
2x baseline or $> 200$		right upper	be restarted
U/L		quadrant	
(whichever occurs first)		pain	

Source: Adapted from Chalasani, Naga and Regev, Arie et al. Drug-Induced Liver Injury in Subjects with Preexisting Chronic Liver Disease in Drug Development: How to Identify and Manage? Gastroenterology, Volume 151. Issue 6, 1046 – 1051

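### In the patient cohorts the Day 29 dose is the only one the hepatic rule can interrupt, yet nothing requires a liver result after Day 15 to be in hand before it, and the next scheduled lab is 28 days later

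*Protocol*

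**What the plan says.** **Doses.** The Protocol synopsis gives the number of doses as "Single dose (Cohorts 1, 2, 3, 4) or two doses (Cohorts 1b, 3b and 4b) dosed 28 days apart". In Table 2 the row "Administration of ARO-HSD" is marked on Day 1 and Day 29 only.

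**Hepatic rule.** The numeric ALT/AST criteria in Protocol Section 7.4 are listed for the healthy-volunteer cohorts. Patients with raised baseline values are referred to Appendix 16.1. Three of the four tiers there call for interruption of study drug. Two of those three add the condition "Study drug can be restarted only if an alternative etiology is identified and liver enzymes return to baseline", which presupposes a later dose.

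**Labs.** Table 2 marks "Labs (heme, coag, chem, lipase, lipids" at screening, Day 1 pre-dose, 24 hours, and Days 15, 29, 57, 71, 85 and 113. In the Day 29 column the pregnancy test and the PK sample are labelled as pre-dose and the ECG has clock times. The labs have a plain mark.

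**Logistics.** Section 7.1 says patients "will be at the facility for approximately 4 hours (2 hours before dosing and 2 hours after dosing) on dosing days". Section 10.3.5 says: "Central labs will be utilized. However, local labs may be utilized as necessary if needed by the investigator or for emergent situations". The same section requires screening results to be assessed before enrollment and a positive pregnancy test to stop dosing. It has no corresponding sentence for Day 29 liver results.

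**Assurance.** Section 5.7 offers the stopping rules as mitigation of hepatic risk and adds: "Blood samples will be drawn frequently to evaluate liver injury and liver function".

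**The concern.** A rule that interrupts treatment needs a current value when treatment is about to be given. Here there is one occasion on which it can act, and the schedule does not secure a value for it. A patient whose ALT crosses an Appendix 16.1 threshold between Day 15 and Day 29 could be dosed again on Day 29, with the result that would have triggered interruption still in transit.

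A second gap follows. Dose 2 is the study's only repeat exposure, yet no visit or lab is scheduled after it until Day 57. A laboratory abnormality counts as an AE only if the investigator judges it clinically significant or it has clinical sequelae (Section 11.2), so a symptomless rise has to be measured before it can be counted. One that came and went between those visits would also be absent from the worst-grade shift tables and the peak-ALT eDISH plot in SAP Section 9.6.2.

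**Working it through.** **Inputs.** Dose and lab days and visit windows come from Protocol Table 2. The SAP Section 5 row "Study Day Window Cohort 1b,3b,4b" gives the same windows: Day 15 [13,17], Day 29 [27,31], Day 57 [55,59]. Time on site before dosing, about 2 hours, is from Section 7.1. Central-laboratory turnaround is not given, so a range of 1 to 72 hours is assumed.

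**Check against the plan's own figures.** Dose interval: 29 − 1 = 28 days, as stated. Patient study duration: 60 + 113 = 173 days, as stated.

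**Age of the Day 15 result at dose 2.**
- Nominal: 29 − 15 = 14 days.
- Shortest: 27 − 17 = 10 days.
- Longest: 31 − 13 = 18 days.

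**Dose 2 to the next scheduled lab.**
- Nominal: 57 − 29 = 28 days.
- Shortest: 55 − 31 = 24 days.
- Longest: 59 − 27 = 32 days.

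The first scheduled lab after dose 1 is at 24 hours.

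**Can a Day 29 sample inform the Day 29 dose?** If blood is drawn on arrival, the result is known in time only if turnaround is no longer than the time before dosing, about 2 hours.

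| Assumed turnaround | Drawn on arrival, about 2 h before dosing | Drawn Day 27, dosed Day 31 (4 × 24 = 96 h) |
|---|---|---|
| 1 h | in time | in time |
| 2 h | in time | in time |
| 6 h | too late | in time |
| 24 h | too late | in time |
| 48 h | too late | in time |
| 72 h | too late | in time |

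The last column shows the most that the existing ±2-day window could provide. No passage provides for splitting draw and dose in this way.

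**How many draws are at stake.** Table 2 has seven post-dose lab draws: 24 hours and Days 15, 29, 57, 71, 85 and 113. Four of them (Days 57, 71, 85 and 113) follow dose 2 and could not inform it under any arrangement. Of the other three, the 24-hour and Day 15 draws precede the dosing visit. The shortfall is 3 − 2 = 1 draw, Day 29.

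**The case against.** The best defence is that the protocol permits what is being asked for. Section 10.3.5 lets an investigator use a local laboratory when needed, so a same-day result is possible. The missing label is weak evidence: the PK row needs one to separate it from the post-dose samples of Day 1, and the pregnancy row because it also carries a pre-biopsy test. Fasting and the two-hour wait fit a draw before dosing, and nothing places the labs after it. All of this stands, but a pre-dose draw is not a pre-dose result, and a permission is not a requirement.

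A reader might go further and infer that the rule acts on Day 15 data. The documents do not support that as a fact. It depends on an unstated turnaround, and a patient who triggers at Day 15 has repeat tests in 2–3 days, or monitoring under the close-observation guidance, so newer values would exist. Those exposed are patients without a trigger at Day 15 who cross a threshold by Day 29.

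A reader might also infer that there is no lab at all until Day 57. That is true only of scheduled labs. A Day 29 result that meets a threshold prompts unscheduled testing, although if it is reported after dosing it is too late to affect that dose.

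The denser sampling in healthy volunteers is a design difference, not a contradiction: they were the first people exposed at each dose. The word used in Section 5.7 sets no interval, so it does not strictly conflict with Table 2 either.

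**Conclusion.** The point holds in a limited form. The only dose that Appendix 16.1 can interrupt in Cohorts 1b, 3b and 4b may be given without a liver result later than Day 15, because no passage requires one. Under the central-laboratory default, the newest scheduled value in hand may be 14 days old (10 to 18). This assumes a turnaround longer than about 2 hours, no local testing and no earlier trigger. One planned draw may fail to serve the rule, and the next scheduled lab is 28 days (24 to 32) after dose 2.

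It would be tempting to conclude that the primary endpoint is compromised. The documents do not support that. AEs are collected continuously to end of study, and what could be missed is limited to a symptomless rise that resolves before Day 57. The documents give no figure for how likely such a rise is, or whether it would be judged a related AE.

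The correction should be made even so: it is cheap, and as written the plan allows a patient who already meets an interruption criterion on Day 29 to be dosed again.

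**What to change.** Reconcile Table 2, Section 10.3.5 and Appendix 16.1 on the timing of the Day 29 liver labs relative to dose 2, so that the Appendix 16.1 rule can operate on the draw already planned. A footnote to Table 2 and one line in Section 10.3.5 would do it, stating when the sample is taken and how its result relates to dosing. No new sample is needed: the existing ±2-day window leaves room to draw ahead of the dose, provided the text says the two may fall on different days, and local testing is already allowed.

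Separately, reconcile the Section 5.7 statement on frequent sampling with the 28-day scheduled gap after dose 2. Rewording alone would make the text accurate but would not detect a silent rise in that interval.

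The cost is a possible extra trip or local-laboratory charge for up to 18 patients (three cohorts of up to 6). Any threshold, dosing decision or added monitoring stays with the sponsor's medical team.
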